15.5 Study time table and end of study

The main part of the study (Visits 1 to 6) is expected to start in Q2 2020 and to be completed by Q2 2021. The follow-up part of the study (Visit 7) is expected to start in Q2 2020 and to be completed by Q3 2021.

A patient is considered to have completed the main part of the study if he/she has completed all visits in the study including Visit 6. The follow-up Visit 7 is a voluntarily visit and the results from this visit will be reported in an addendum to the CSR.

[figure not shown]
The end of the study is defined as the date of the last Visit 7 of the last patient in the study.

15.6 **Termination of the study**

The Investigator or the Sponsor may terminate this study prematurely for any reasonable cause. The IEC and CA should be informed promptly. Conditions that may warrant study termination include, but are not limited to:

- The discovery of an unexpected, significant, or unacceptable risk to the patients enrolled in the study or potential study patients; or
- A decision by the Sponsor to suspend or discontinue development of the IMP.
- If the CA obtains information that raises doubts about the safety or scientific validity of the clinical study, the CA can suspend or prohibit the study. Before the CA reaches its decision, it shall, except where there is imminent risk, ask the Sponsor and/or the

CONFIDENTIAL 77 (92)

Investigator for their opinion, to be delivered within one week (Directive 2001/20/EC, Article 12, Section 1).

If the study is prematurely terminated or suspended for any reason, the Investigator/institution should promptly inform the study patients and should assure appropriate follow-up for the patients.

15.7 Reporting and publication

15.7.1 Clinical study report

A summarising report must be submitted to the applicable CA and IEC within 12 months after completion of the study (in accordance with LVFS 2011:19, Chapter 9).

A CSR, in compliance with ICH-E3, describing the conduct of the study, any statistical analyses performed, and the results obtained, will be prepared by CTC. The report will be reviewed and approved by, as a minimum, the Principal Investigator, the Statistician and the Sponsor. The study results will be reported in the EudraCT database per applicable regulations within 12 months after completion of the study.

All data obtained from exploratory analyses will be reported separately.

15.7.2 Annual safety report

If the study duration exceeds one year, the Sponsor must submit development safety update report (DSUR) to the CA and to the IEC. The report shall summarise all pertinent safety information collected during the reporting period and contain an update of the risk-benefit evaluation if there has been any change since the approval of the clinical study.

15.7.3 Confidentiality and ownership of study data

Any confidential information relating to the IMP or the study, including any data and results from the study, will be the exclusive property of the Sponsor. The Investigator and any other persons involved in the study are responsible for protecting the confidentiality of this proprietary information belonging to the Sponsor.

15.7.4 Publication

The results from this study may be submitted for publication at the discretion of the Sponsor.

15.8 Archiving

The Principal Investigator is responsible for maintaining essential documents, (as defined in ICH E6 GCP, Section 8) for 10 years after finalisation of the CSR. This includes any original source documents related to the study, the Patient Identification List (providing the sole link between named patient source records and anonymous eCRF data), the original signed ICFs and detailed records of disposition of IMP.

CONFIDENTIAL 78 (92)

Clinical Study Protocol EP-002 Final version v3.0 12NOV2020

It is the responsibility of the Sponsor to inform the Investigator/institution as to when these documents no longer need to be retained.

The Sponsor will archive the TMF in accordance with ICH E6 GCP, Section 8 and applicable regulatory requirements.

The data from the eCRFs will be sent to the Sponsor and a copy will be sent to the clinic and filed in the Investigator Study File for archiving for 10 years after finalisation of the CSR.

The completed eCRFs are the sole property of the Sponsor and should not be made available in any form to third parties, except for authorised representatives of appropriate Health/Regulatory Authorities, without written permission from the Sponsor.

16 DATA MANAGEMENT

The data management routines include procedures for handling of the eCRF, database set-up and management, data entry and verification, data validation, QC of the database, and documentation of the performed activities including information of discrepancies in the process. The database, data entry screens, and program will be designed in accordance with the CSP.

Data validation/data cleaning procedures are designed to assure validity and accuracy of clinical data. These procedures consist of computerised online edit checks identifying e.g. data values that are outside the allowed range and SAS-programmed batch checks on data exports. All study-specific and standard data validation programming will be tested in a separate testing environment prior to use on production data.

Detailed information on data management will be described in a study-specific Data Management Plan (DMP).

16.1 The web-based eCRF

Clinical data will be entered into a 21 CFR Part 11-compliant eCRF (ViedocTM) provided by PCG Solutions AB. The eCRF includes password protection and internal quality checks, such as automatic range checks, to identify data that appear inconsistent, incomplete, or inaccurate. Clinical data will be entered directly from the source documents or at bedside (if the eCRF data constitutes source data). Source data are to be defined at the site before inclusion of the first patient (Section 15.3).

Authorised site personnel designated by the Investigator will complete data collection. Appropriate training and security measures will be completed with the Investigator and all authorised trial site personnel prior to the trial being initiated and any data being entered into the system for any study patient.

16.2 The entering of data into the eCRF

All entries, corrections, and alterations are to be made by the Investigator or designee. Neither the Monitor nor any other study team member besides site staff can enter data in the eCRF. All data should be entered in English. The eCRFs should be completed as soon as possible

CONFIDENTIAL 79 (92)

during or after the patient's visit. The Investigator must verify that all data entries in the eCRFs are accurate and correct. If some assessments are not done, or if certain information is not available, not applicable or unknown, the Investigator or assigned clinical staff should record such information in the eCRF. The Investigator will be required to electronically sign off the clinical data. This will be performed by means of the Investigator's unique User ID and password; date and time stamps will be added automatically at time of electronic signature.

16.3 Electronic patient reported outcome

The patients themselves will record data (see Section 11.2) using an ePRO system (ViedocMe™) linked to the eCRF. The ePRO system includes password protection and internal quality checks. Text reminders can be sent to the patient through the ePRO. All data registered in the ePRO are stored together with the eCRF data.

16.4 The query process

The Monitor will review the eCRFs and evaluate them for completeness and consistency. Data in the eCRF will be compared with the respective source documents to ensure that there are no discrepancies for critical data as described in the RBM plan. All entries, corrections, and alterations are to be made by the Investigator or designee. Neither the Monitor nor any other study team member besides site staff can enter data in the eCRF.

If corrections are needed, queries will be raised within the eCRF, either as a result of built-in edit checks or manually raised by the monitor. An appropriate member of the site staff will answer the queries in the eCRF either by correcting the data or by entering a response to the query. The monitor will either approve the answer/correction or re-issue the query.

16.5 Audit trail

All entries in the eCRF will be fully recorded in a protected audit trail. Once clinical data have been saved, corrections to the data fields will be audit trailed, meaning that the reason for change, the name of the person who made the change, together with time and date will be logged.

16.6 External data

External data consists of data that are not recorded in the eCRF. Data may be received in electronic format or as a paper printout. Key variables are defined in order to uniquely identify each sample record. File and data formats are agreed with the external data provider.

16.7 **Medical coding**

Medical coding will be performed by trained personnel at CTC. AEs and medical/surgical history verbatim terms will be coded using the Medical Dictionary of Regulatory Activities

CONFIDENTIAL 80 (92)

Clinical Study Protocol EP-002 Final version v3.0 12NOV2020

(MedDRA; latest version available at start of coding). Prior and concomitant medications will be coded according to the World Health Organisation (WHO) Anatomic Therapeutic Chemical (ATC) classification system. All coding will be approved by Sponsor prior to database lock.

16.8 **Database lock**

When all data in the main part (Visits 1 to 6) have been entered and all discrepancies are solved, clean file will be declared, the database will be locked, the code will be broken and the data will be analysed. The CSR will be written based on the main part (Visits 1 to 6).

When data from the follow-up part (Visit 7) have been entered and all discrepancies are solved, clean file for Visit 7 will be declared, the database will be locked, the data will be analysed and presented in an addendum to the CSR.

17 STATISTICAL METHODS AND DETERMINATION OF SAMPLE SIZE

The principal features of the statistical analysis to be performed are described in this section. A more technical and detailed elaboration of the principal features will be presented in a separate Statistical Analysis Plan (SAP), which will be signed and approved prior to database lock.

Analyses of the primary and secondary endpoints will be performed by CTC AB.

17.1 General

Continuous data will be presented in terms of evaluable and missing observations, arithmetic mean, standard deviation (SD), median, minimum and maximum value.

Categorical data will be presented as counts and percentages. When applicable, summary data will be presented by treatment, and by assessment time. Individual patient data will be listed by patient number, treatment, and, where applicable, by assessment time.

All descriptive summaries and statistical analyses will be performed using SAS Version 9.4 or later (SAS Institute, Inc., Cary, NC).

Baseline will be defined as the visit with last data collection point prior to the first administration of IMP.

Outliers will be included in summary tables and listings and will not be handled separately in any analyses. No imputation of data will be performed neither for dropouts nor for missing data. An analysis of dropouts will be performed as detailed in Section 17.6.6.

All hypothesis testing will use a significance level of 5%.

Comparisons will be made pairwise and analysed at each visit if not stated otherwise.

CONFIDENTIAL 81 (92)

17.2 **Determination of sample size**

The hypothesis is to show that patients treated with EMP16-02 have a greater relative change (reduction) in body weight compared to placebo. The estimated treatment difference should be 5% with a standard deviation of 8%, a power of 80% and a significance level of 5% based on two-sided hypothesis testing. Using PASS V16.0 (method compare means), the number of evaluable patients needed per treatment arm is calculated to 41 patients. An evaluable patient is defined as a patient who has completed 26 weeks of treatment with IMP. Taking into account an estimated drop-out frequency of 20%, a total of 156 patients need to be randomised.

17.3 Analysis data sets

17.3.1 Full analysis set

The Full Analysis Set (FAS) will consist of all patients who have been randomised and received at least one dose of IMP and who have at least one post-baseline assessment of efficacy data.

17.3.2 Safety analysis set

The Safety Analysis Set will consist of all patients who received at least one dose of the IMP.

17.3.3 Per protocol set

The Per Protocol Set (PPS) will consist of all patients who have been randomised and completed the study without any major protocol deviations that are judged to compromise the analysis of the data. All protocol violations will be judged as major or minor prior to database lock.

17.4 **Description of study population**

17.4.1 Demographics and baseline characteristics

Descriptive statistics for demographics, weight and height, BMI, waist circumference, sagittal diameter and body composition will be presented by treatment.

17.4.2 Medical/obesity history and prior/concomitant medication

Medical/obesity history will be presented by treatment, system organ class (SOC) and preferred term (PT). Prior/concomitant medications will be presented by treatment and applicable ATC level.

All data will be listed by treatment and patient.

CONFIDENTIAL 82 (92)

17.4.3 Baseline symptoms

Baseline symptoms will be presented by treatment, SOC and PT. All data will be listed by treatment and patient.

17.4.4 Treatment compliance

Compliance will be calculated by counting tablets, as follows:

$$compliance = \frac{number\ of\ delivered\ capsules - number\ of\ returned\ capsules}{number\ of\ delivered\ capsules}$$

17.5 Analysis of primary endpoints

17.5.1 Weight

Relative (%) change from baseline in body weight after 26 weeks of treatment with EMP16-02 (120 mg O/40 mg A) as compared to placebo will be analysed using analysis of variance with treatment as independent variable.

17.6 Analysis of secondary endpoints – efficacy

17.6.1 Weight

The absolute change from baseline in body weight after 14 and 26 weeks of treatment with EMP16-02 (120 mg O/40 mg A) as compared to placebo will be analysed using analysis of covariance with treatment and body weight at baseline as covariates.

The relative (%) change from baseline in body weight after 14 and 26 weeks of treatment with EMP16-02 (150 mg O/50 mg A) as compared to placebo will be analysed using analysis of variance with treatment as independent variable.

The proportion of patients with \geq 5% and \geq 10% decrease in body weight compared to baseline after 14 and 26 weeks of treatment with EMP16-02 (120 mg O/40 mg A and 150 mg O/50 mg A) as compared to placebo will be analysed using Chi-square test without continuity correction.

17.6.2 Anthropometric measurements

The relative change from baseline in BMI after 14 and 26 weeks of treatment with EMP16-02 (120 mg O/40 mg A and 150 mg O/50 mg A) as compared to placebo will be analysed using analysis of variance with treatment as independent variable. Baseline is defined as BMI measured pre-dose at Visit 2. The absolute change from baseline in BMI will be analysed using analysis of covariance with treatment and body weight at baseline as covariates.

The absolute change from baseline in waist circumference after 14 and 26 weeks of treatment with EMP16-02 (120 mg O/40 mg A and 150 mg O/50 mg A) as compared to placebo will be analysed using analysis of covariance with treatment and body weight at baseline as covariates.

CONFIDENTIAL 83 (92)

Clinical Study Protocol EP-002 Final version v3.0 12NOV2020

The absolute change from baseline in sagittal diameter after 14 and 26 weeks of treatment with EMP16-02 (120 mg O/40 mg A and 150 mg O/50 mg A) as compared to placebo will be analysed using analysis of covariance with treatment and body weight at baseline as covariates.

The relative (%) change from baseline in percentage body fat after 14 and 26 weeks of treatment with EMP16-02 (120 mg O/40 mg A and 150 mg O/50 mg A) as compared to placebo will be analysed using analysis of variance with treatment as independent variable. The absolute change from base line in percentage of body fat will be analysed using analysis of covariance with treatment and body weight at baseline as covariates.

17.6.3 Glucose metabolism markers, lipid metabolism markers and inflammation markers

Fasting HbA1c, glucose, insulin, total cholesterol, HDL, LDL, triglycerides, liver enzymes, albumin and hs-CRP will be assumed to be normally distributed.

The relative (%) change from baseline in fasting HbA1c, glucose, insulin, total cholesterol, HDL, LDL, triglycerides, liver enzymes, albumin and hs-CRP after 7, 14 and 26 weeks of treatment with EMP16-02 (120 mg O/40 mg A and 150 mg O/50 mg A) as compared to placebo will be analysed using analysis of variance with treatment as independent variable. The absolute change from baseline in these markers will be analysed using analysis of covariance with treatment and body weight at baseline as covariates.

The proportions of diabetic patients (patients with a fasting glucose ≥ 7.0 mmol/L) and prediabetic patients (fasting glucose ≥ 6.1 and < 7.0 mmol/L) and non-diabetic patients (fasting glucose < 6.1 mmol/L) after 14 and 26 weeks of treatment with EMP16-02 (120 mg O/40 mg A and 150 mg O/50 mg A) will be presented using shift tables. The change from baseline in the proportion of diabetic and prediabetic patients after 14 and 26 weeks of treatment with EMP16-02 as compared to placebo will be analysed using Chi-square test without continuity correction.

17.6.4 **Blood pressure**

The relative (%) change from baseline in blood pressure after 14 and 26 weeks of treatment with EMP16-02 (120 mg O/40 mg A and 150 mg O/50 mg A) as compared to placebo will be analysed using analysis of variance with treatment as independent variable. The absolute change from baseline in blood pressure will be analysed using analysis of covariance with treatment and body weight at baseline as covariates.

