17.6.5 Questionnaires

17.6.5.1 Meal pattern questionnaire

For each treatment group, the absolute and percent change from baseline in total score of the Meal pattern questionnaire will be calculated and analysed using the Wilcoxon Rank Sum test at each visit. The absolute change for each question will be compared between the treatment groups by using the Wilcoxon Rank Sum test.

CONFIDENTIAL 84 (92)

Clinical Study Protocol EP-002 Final version v3.0 12NOV2020

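### Section 17.6.3 assumes normality for right-skewed markers and ignores their own baseline values, which biases mean % change upward and loses power, mainly for hs-CRP

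*Protocol*

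**What the plan says.** Section 17.6.3 opens with a distributional rule for ten markers or marker groups: "Fasting HbA1c, glucose, insulin, total cholesterol, HDL, LDL, triglycerides, liver enzymes, albumin and hs-CRP will be assumed to be normally distributed". No check, transformation or rank-based alternative follows.

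Two tests are then fixed for weeks 7, 14 and 26:

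- Relative change is "as compared to placebo will be analysed using analysis of variance with treatment as independent variable. The absolute change from baseline in these markers" are handled separately, as the next point shows.
- For absolute change: "The absolute change from baseline in these markers will be analysed using analysis of covariance with treatment and body weight at baseline as covariates". The covariate is body weight, not the marker's baseline value.

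Section 17.1 adds: "Outliers will be included in summary tables and listings and will not be handled separately in any analyses". On description it says: "Continuous data will be presented in terms of evaluable and missing observations, arithmetic mean, standard deviation (SD), median, minimum and maximum value". Medians are therefore planned; quartiles and geometric means are not.

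The protocol does use rank tests elsewhere. For the meal pattern items: "The absolute change for each question will be compared between the treatment groups by using the Wilcoxon Rank Sum test". Sections 17.6.5.3 and 17.6.5.5 do the same for satiety and craving and for RAND-36. It also defers some details openly to the SAP: further GSRS covariates (17.6.5.2), single satiety questions (17.6.5.3), ApoA1/ApoB and plasma levels (17.8.1, 17.8.2). The marker analysis is not deferred; distribution and test are both stated.

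**The concern.** hs-CRP, triglycerides, insulin and liver enzymes are positive concentrations with a long upper tail. An individual % change cannot fall below -100% but has no upper limit, so its arithmetic mean is pulled up by patients with a low baseline or a transient rise. The planned ANOVA tests that mean, and its variance is inflated by the same tail. Neither planned model uses the marker's own baseline, which is collected in any case and usually explains much of the follow-up variation.

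These markers serve a stated secondary objective, at three visits and for two doses, in a study meant as proof of concept. At stake are misleading within-arm summaries and missed effects on inflammation and metabolic markers. The primary endpoint is not touched.

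**Working it through.** **The plan's own figure.** Section 17.2 gives a difference of 5%, SD 8%, 80% power and two-sided 5%. By the normal approximation n = 2 × (1.960 + 0.842)² × 8² / 5² = 40.2, so 41 per arm; power at 41 is 80.8% (normal) or 79.8% (t). Then 41 / 0.80 = 51.25, so 52 per arm and 156 in total. The plan's numbers reproduce. No power is stated for the markers, so 41 per arm is used below.

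**Assumptions (not in the protocol).** Baseline and follow-up are bivariate log-normal with log-SD σ at both times and correlation ρ. The drug multiplies follow-up by a ratio R.

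**Bias of the arm mean.** The log ratio has variance s² = 2σ²(1 - ρ). Expected mean % change is 100 × (R·exp(s²/2) - 1); the median is 100 × (R - 1).

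- hs-CRP-like, σ = 1.0, ρ = 0.6: s² = 0.80 and exp(0.40) = 1.49. Placebo (R = 1): +49%, median 0. Active (R = 0.65): 0.65 × 1.49 = 0.97, so -3%, median -35%.
- Triglyceride/insulin-like, σ = 0.6, ρ = 0.6: s² = 0.288 and exp(0.144) = 1.155. Placebo: about +15%. Active (R = 0.80): 0.924, so -8%, median -20%.
- hs-CRP-like with 3% of follow-up values raised tenfold and kept: the mean ratio is multiplied by 1 + 0.03 × 9 = 1.27. Active: 0.65 × 1.49 × 1.27 = 1.23, so about +23% (simulation: +24%) despite a true 35% fall.

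**Power at 41 per arm, by simulation, two-sided 5%.** Log change separates the effect of the scale from that of baseline adjustment.

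| Scenario | % change ANOVA | Log change | Log-ANCOVA |
|---|---|---|---|
| hs-CRP-like (σ 1.0, ρ 0.6, R 0.65) | 44% | 57% | 67% |
| Same, 3% tenfold outliers kept | 24% | 50% | 58% |
| Triglyceride/insulin-like (σ 0.6, ρ 0.6, R 0.80) | 41% | 46% | 54% |

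For hs-CRP, 57 - 44 = 13 of the 23 points come from the scale and 10 from baseline adjustment. For the second marker, 46 - 41 = 5 of 13 come from the scale and 8 from baseline adjustment.

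**Range over other assumed values, clean data, same column order.**

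- hs-CRP (σ 0.9-1.1, ρ 0.6-0.7, R 0.65): 44-70%, 58-79%, 67-85%; placebo mean +28% to +49%.
- Triglycerides (σ 0.45-0.5, ρ 0.6-0.7, R 0.80): 67-70%, 70-73%, 79%; placebo mean +8% to +9%.
- Insulin (σ 0.55, ρ 0.7, R 0.75): 83%, 86%, 90%; placebo mean +10%.
- ALT (σ 0.45, ρ 0.7, R 0.85): 52%, 55%, 61%; placebo mean +6%.

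With no true effect, the % change ANOVA rejected in 4.4% to 4.9% of runs for these markers. For HbA1c and glucose (log-SD 0.1) the scale made no difference. Absolute change in the first scenario gave 28%, but from an unadjusted t-test; the planned body-weight covariate was not modelled, so that figure is only indicative.

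**The case against.** The strongest reply is that these are secondary markers in a study that calls itself exploratory, the tests hold their level, and the median, minimum and maximum are already tabulated, so a skewed mean would be visible. All of that stands. It softens the descriptive problem but does not restore lost power. It is also fair that every size here rests on assumed inputs, and that for triglycerides, insulin and liver enzymes the scale alone costs only about 2 to 5 points on clean data.

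Three stronger readings are tempting and not supported:

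- **Both arms will show rises.** At the central values the active arm shows a fall (-3% and -8%). A rise there needs little or no drug effect, gross outliers, or a weaker correlation (ρ = 0.5 gives 0.65 × exp(0.5) = 1.07 for hs-CRP). The protocol fixes none of these.
- **A true reduction versus placebo is masked.** The endpoint is a comparison with placebo. On log-normal data both arms are inflated by the same factor, so the contrast is enlarged: 49 - (-3) = 52 points for a true 35% reduction. The arm means mislead; the difference is not hidden.
- **One infection-related value can decide the comparison.** One very large value M among n per arm shifts the mean difference by about M/n and makes the standard error about M/n as well, so |t| tends to 1. It can cost significance but is unlikely to create it.

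**Conclusion.** The point holds in limited form. The protocol itself states a distribution that does not suit four of its marker groups, and it omits the one covariate most likely to help. The consequences are upward-biased arm means for % change and lost power, with no inflation of false positives.

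The loss is large for hs-CRP: 23 points against log-ANCOVA on clean data in the main scenario, and 58 - 24 = 34 points with 3% tenfold outliers kept. It is modest for triglycerides, insulin and liver enzymes on clean data, at about 7 to 13 points against log-ANCOVA, most of it due to the missing baseline adjustment. The direction is secure; the figures depend on assumed log-SDs, correlations, effects and outlier rates. The primary endpoint and the sample size are unaffected. This should be changed, but it does not threaten the trial.

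**What to change.** In Section 17.6.3, delete the blanket normality sentence. For hs-CRP first, and also for triglycerides, insulin and liver enzymes, analyse log(value) at each visit by ANCOVA with treatment and log(baseline value). Report the geometric mean ratio versus placebo with 95% CI as the relative-change result; (ratio - 1) × 100 expresses it as a percentage. Add quartiles to the planned medians. Align the matching paragraph in the synopsis.

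The cost is wording in the protocol and SAP; no patients, visits or samples are added. Section 17 places SAP approval before database lock, so the change can be made blinded. The downside is that results for these markers read as ratios rather than arithmetic mean % changes.

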The proportion of patients with \geq 5% and \geq 10% decrease in body weight compared to baseline after 14 and 26 weeks of treatment with EMP16-02 (120 mg O/40 mg A and 150 mg O/50 mg A) as compared to placebo will be analysed using Chi-square test without continuity correction.

Other anthropometric parameters, glucose metabolism markers, lipid metabolism markers, inflammation markers and blood pressure will also be analysed using analysis of variance. For

CONFIDENTIAL 8 (92)

Clinical Study Protocol EP-002 Final version v3.0 12NOV2020

relative changes from baseline, treatment will be used as independent variable. For absolute changes from baseline, treatment and body weight will be used as covariates.

The proportions of diabetic patients, prediabetic patients and non-diabetic patients after 14 and 26 weeks of treatment with EMP16-02 (120 mg O/40 mg A and 150 mg O/50 mg A) will be presented using shift tables. The change from baseline in the proportion of diabetic and prediabetic patients after 14 and 26 weeks of treatment with EMP16-02 as compared to placebo will be analysed using Chi-square test without continuity correction.

Meal pattern, satiety and craving and health and quality of life (RAND-36) questionnaires will be analysed using the Wilcoxon Rank Sum test. The GSRS questionnaire will be analysed using analysis of covariance while the activity and sleep questionnaire will be analysed using a Chi-square test. The drop-out rate (overall and GI-related) following treatment with EMP16-02 (120 mg O/40 mg A and 150 mg O/50 mg A) as compared to placebo will be analysed using Chi-square test without continuity correction.

Continuous data will be presented in terms of evaluable and missing observations, arithmetic mean, standard deviation (SD), median, minimum and maximum value.

Categorical data will be presented as counts and percentages. When applicable, summary data will be presented by treatment, and by assessment time. Individual patient data will be listed by treatment, patient number, and, where applicable, by assessment time.

All descriptive summaries and statistical analyses will be performed using SAS Version 9.4 or later (SAS Institute, Inc., Cary, NC).

Baseline is defined as the visit with last data collection point prior to the first administration of IMP.

All hypothesis testing will use a significance level of 5%.

Comparisons will be made pairwise and analysed at each visit if not stated otherwise.

Study reporting

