17.6.5.2 Gastrointestinal tolerability questionnaire

For each treatment group, the absolute and percent change from baseline in total score of the GSRS be calculated and analysed using analysis of covariance with at least treatment, weight at baseline as covariates. More covariates will be addressed in the SAP.

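### Absolute-change ANCOVAs for BMI, waist, sagittal diameter, body fat, laboratory markers and blood pressure adjust for baseline body weight, not the variable's own baseline, which costs precision

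*Protocol*

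**What the plan says.** The protocol fixes the covariates for absolute changes in several places:

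- Section 17.6.3, for HbA1c, glucose, insulin, lipids, liver enzymes, albumin and hs-CRP: "The absolute change from baseline in these markers will be analysed using analysis of covariance with treatment and body weight at baseline as covariates".
- Section 17.6.4: "The absolute change from baseline in blood pressure will be analysed using analysis of covariance with treatment and body weight at baseline as covariates".
- Section 17.6.2, for waist circumference and sagittal diameter: "as compared to placebo will be analysed using analysis of covariance with treatment and body weight at baseline as covariates". BMI and percentage body fat get the same model.
- Synopsis, Statistical methods, as a general rule: "For absolute changes from baseline, treatment and body weight will be used as covariates".
- Sections 17.8.4 and 17.8.5, for HbA1c and blood pressure 6 months after treatment: treatment and body weight, with no time point given for the weight.

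The variable's own baseline is named in none of these. Among the absolute-change models, only those for body weight itself have a weight covariate that belongs to the outcome (17.6.1, 17.8.3).

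The GSRS model in 17.6.5.2 is worded differently: "analysis of covariance with at least treatment, weight at baseline as covariates". The next sentence there leaves further covariates to the SAP.

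On testing, Section 17.1 says: "All hypothesis testing will use a significance level of 5" per cent.

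**The concern.** A change score contains the baseline value with a minus sign, so it correlates with that baseline through regression to the mean. Adjusting for the baseline removes this component from both the error variance and the treatment contrast. Body weight removes it only as far as weight tracks the variable. Nothing in the protocol suggests close tracking for LDL, HbA1c, hs-CRP or blood pressure.

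These baselines can be expected to vary. Inclusion criterion 3 admits treated and untreated hypertension and dyslipidaemia, and type 2 diabetes managed without medication. Section 9.9 gives 1:1:1 randomisation and names no stratification factor, so nothing restricts chance imbalance in these variables.

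At stake are larger standard errors than the data require for a block of declared secondary endpoints, and estimates that move with chance baseline differences.

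**Working it through.** **The plan's own figure.** Section 17.2: "The estimated treatment difference should be 5% with a standard deviation of 8%, a power of 80% and a significance level of 5" per cent, "based on two-sided hypothesis testing".

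- n per arm = 2 × (1.96 + 0.8416)² × (8/5)² = 2 × 7.849 × 2.56 = 40.2, so 41. The noncentral t gives 79.8% power at 41.
- With 20% drop-out, 41/0.8 = 51.25, so 52 per arm and 3 × 52 = 156.

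The stated 41 and 156 reproduce. They concern relative change in body weight, so the covariate question does not touch them.

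**Inputs for the covariate question.** The protocol gives no correlations or SDs for these variables, so the following are assumptions:

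- r, the correlation of the variable's baseline with its follow-up: 0.3 to 0.9.
- q, the correlation of the variable's baseline with baseline body weight: 0 to 0.8.
- Equal (unit) variances at baseline and follow-up.
- Weight predicts follow-up only through the variable's own baseline.

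**Residual variance of the change.**

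- Adjusted for weight: 2(1 − r) − q²(1 − r)².
- Adjusted for own baseline: 1 − r².
- Ratio: [2 − q²(1 − r)] / (1 + r).

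Example with r = 0.5 and q = 0.3: (2 − 0.09 × 0.5)/1.5 = 1.955/1.5 = 1.30.

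| r | ratio, q = 0 | ratio, q = 0.3 | ratio, q = 0.8 |
|---|---|---|---|
| 0.3 | 1.54 | 1.49 | 1.19 |
| 0.5 | 1.33 | 1.30 | 1.12 |
| 0.7 | 1.18 | 1.16 | 1.06 |
| 0.8 | 1.11 | 1.10 | 1.04 |
| 0.9 | 1.05 | 1.05 | 1.02 |

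At q = 0.3, matching 41 per arm with own-baseline adjustment would take about 61, 53, 48, 45 and 43 per arm, reading down the rows. A comparison with 80% power under own-baseline adjustment would have about 63%, 69%, 74%, 76% and 78%. These are illustrations, because the protocol powers only body weight.

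**Chance imbalance.** If the arms differ by b in the variable's baseline and weight is balanced, the weight-adjusted estimate carries −(1 − r)b: −0.5b at r = 0.5 and −0.2b at r = 0.8. The standard error of b with 41 per arm is √(2/41) = 0.22 SD, so a 0.2 SD difference is ordinary. It would leave 0.2 × 0.5 = 0.10 SD at r = 0.5 and 0.2 × 0.3 = 0.06 SD at r = 0.7.

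**Simulation** (41 per arm, 4,000 runs per setting; r = 0.5, 0.7, 0.8; q = 0.3, 0.8).

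- Both estimators averaged close to zero with no true effect (between −0.001 and 0.005), so neither is biased on average.
- Variance ratios at q = 0.3 were 1.28, 1.15 and 1.10. At q = 0.8 they were 1.15, 1.06 and 1.03.
- The weight-adjusted estimate moved with own-baseline imbalance (slope −0.44 at r = 0.5 and −0.27 at r = 0.7, both q = 0.3). The own-baseline-adjusted estimate did not (slope about 0).

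**The case against.** Several points on the other side stand:

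- **The test remains valid.** Allocation is randomised, so the weight-adjusted contrast is unbiased on average. A reader might infer systematic bias, or that a baseline difference carries over in full. Neither follows: the problem is conditional on chance imbalance, and only about 1 − r of the imbalance remains.
- **Weight is a partial proxy for some variables.** For waist or sagittal diameter q may be high. At q = 0.8 the variance inflation is only 2% to 19%.
- **The size depends on equal variances.** Measured against the raw change (q = 0), the proportional variance reduction from own-baseline adjustment is (s₁ − r·s₂)² / Var(change), with s₁ and s₂ the baseline and follow-up SDs. At r = 0.7 it is 0.3²/0.6 = 15% when s₂ = s₁. When s₂ = 1.2·s₁ it is 0.16²/0.76, about 3%. With s₂ below s₁ it is larger.
- **The study calls itself exploratory**, and its primary analysis is untouched.

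Two wider readings are tempting but unsupported. The first takes in the GSRS. Section 17.6.5.2 sets only a minimum covariate list and defers the rest to the SAP, so GSRS baseline is not excluded. The second treats the absence of a covariate in the relative-change ANOVAs as the same defect. Percent change is already scaled to baseline, ANOVA on it is a valid randomised comparison, and the figures above do not measure that choice.

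The reply that covariates are a matter for the SAP does not succeed for 17.6.2 to 17.6.4. Their lists are closed, and Section 17 describes the SAP as elaborating these features. The GSRS wording shows how the protocol marks a deferral when it intends one.

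**Conclusion.** The point holds for absolute change in BMI, waist circumference, sagittal diameter, percentage body fat, the laboratory markers and blood pressure, and for 6-month HbA1c and blood pressure. The stated covariate is a poor choice. The consequence is lost precision and sensitivity to chance baseline imbalance.

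Under the assumptions listed, the variance is about 2% to 54% larger than it need be. The loss is greatest where r is low and weight tells little about the variable. It is slight where r is high or the variable follows weight closely. The direction is well supported, but the size for any one endpoint is uncertain because the protocol gives no correlations or SDs for these variables, and unequal variances can move it outside this range. The change should be made, although the trial's main conclusion does not depend on it.

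**What to change.** - In 17.6.2, 17.6.3, 17.6.4 and the synopsis rule, name the Visit 2 baseline value of the variable analysed as the covariate for absolute change. Baseline body weight may stay as a second covariate.
- In 17.8.4 and 17.8.5, do the same. For change from week 26, also use the pre-treatment Visit 2 value, because the week-26 value is itself affected by treatment. If weight is kept there, state that it is baseline weight.
- Leave the body-weight models (17.6.1, 17.8.3) and the open GSRS list (17.6.5.2) as they are.

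The cost is wording only. The schedule of events already collects all these variables at Visit 2, and the sample size does not change. Making the change before unblinding avoids a post-hoc choice of covariate.
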